9.5.5 Safety Endpoint

Primary safety endpoint is the proportion of participants experiencing any Grade 2 or higher clinical AEs or laboratory abnormalities since the initial injection to 12 weeks (8 weeks) after the last injection in Cohort 1 (Cohort 2) among the participants who complete at least one injection to evaluate the safety of the 744 injectable during the injection phase. A secondary safety endpoint is the proportion of Grade 2 or higher clinical AEs or laboratory abnormalities occurred from the initial injection to 76 weeks in both cohorts after last injection among the participants who complete at least one injection to evaluate the safety of the 744 injectable in long term; the proportion of Grade 2 or higher AEs or laboratory abnormalities occurred during the oral phase (Weeks 0-5) among all enrolled participants to evaluate the safety of the oral 744 product; and the proportion of Grade 2 or higher AEs or laboratory abnormalities occurred during the whole study period among the all enrolled participants to evaluate the safety of the oral and injectable product. The proportions of endpoints and the %95 confidence intervals will be estimated for each treatment arm. The 95% CIs will be estimated using Wilson score method¹. The proportions of endpoints will be compared between the treatment arms using Fisher Exact test.

In addition, the safety endpoint rate might be calculated for each treatment arm and compared between the treatment arms. The safety endpoint rate is the number of the participants who have experienced Grade 2 or higher clinical AEs or laboratory abnormalities during the study period (defined in each safety analysis) divided by the person-time-at-risk throughout the observation period within the study period.

The 95% exact confidence interval of the safety event rate will be calculated for each treatment arm, assuming the rate follows the Poisson distribution. The safety event rate will be compared between the treatment arms using exact Poisson test.

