4.3 Study Duration

Approximately 3 years. Accrual will require approximately 16 to 24 weeks (4 – 6 months) for each cohort. Study participants in both cohorts will receive oral tablets for 4 weeks, followed by a 1 week wash out period. Cohort 1 will then receive intra-muscular injections at 3 time points over 24 weeks (6 months); cohort 2 will receive intra-muscular injections at five time points over 28 weeks (7 months). Participants in the active study product arm will be followed for 76 weeks (18 months) after their last injection. Participants in the placebo arm will be followed until 76 weeks after their last injection or until the last participant in the active study product arm in cohort 2 completes their Week 41 visit, whichever comes first, at which time the study will be unblinded to assess the primary endpoint. When all procedures related to unblinding are completed, participants in the placebo arm will no longer be followed.

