4.8 Blinding

Study site staff, with the exception of the site Pharmacist of Record or their designee, and participants will be blinded to the random assignments. Blinding will be maintained until the last participant enrolled in to the active drug arm in cohort 2 has completed their Week 41 visit (the time point of the primary endpoint of the study), and when all data related to the Week 41 visit has been entered into the database, as well as cleaned and verified. At a specified time directed by the HPTN SDMC, participants will be unblinded to their treatment assignment, and participants in the placebo arm will no longer need to be followed. Participants in the active study product arm will continued to be followed for 52 weeks after their last injection.

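### The 76-week and whole-study Grade 2+ proportions are Fisher-tested between arms although placebo follow-up stops at unblinding, which tilts both comparisons towards more AEs on active

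*SAP*

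**What the plan says.** SAP 9.5.5 lists the primary safety proportion and several secondary ones. Two of these run past Week 41. One, among injected participants, counts Grade 2 or higher AEs or "laboratory abnormalities occurred from the initial injection to 76 weeks in both cohorts after last injection". The other counts AEs or "laboratory abnormalities occurred during the whole study period among the all enrolled participants". One sentence then covers every proportion in the list: "The proportions of endpoints will be compared between the treatment arms using Fisher Exact test". No common cut-off and no censoring rule is given.

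On follow-up, SAP 4.3 states: "Participants in the active study product arm will be followed for 76 weeks (18 months) after their last injection". Placebo participants stop at the earlier of 76 weeks after the last injection or the Week 41 visit of the last active participant in Cohort 2. Then: "When all procedures related to unblinding are completed, participants in the placebo arm will no longer be followed". SAP 4.8 repeats the release at unblinding and places it after the last such visit "and when all data related to the Week 41 visit has been entered into the database, as well as cleaned and verified". It gives a different tail for the active arm: "Participants in the active study product arm will continued to be followed for 52 weeks after their last injection".

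The only adjustment for exposure in 9.5.5 is introduced as optional: "In addition, the safety endpoint rate might be calculated for each treatment arm and compared between the treatment arms".

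**The concern.** The two arms are observed for different lengths of time by design, not through chance dropout. A crude proportion with at least one event accumulates over time, so the arm watched longer records more first events even when the hazards are identical. The two long-term p-values therefore mix any drug effect with the difference in follow-up.

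The person-time rate does not settle the matter. Events divided by time to first event gives an unbiased comparison across unequal follow-up only if the hazard is constant. If AE risk falls once injections stop, the active arm contributes proportionally more low-risk time and its rate is pulled down. The Fisher test then leans towards harm and the rate test towards benefit, so the two analyses can disagree with no drug effect at all.

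**Working it through.** **The SAP's own timeline.** Last injection plus 76 weeks is 29 + 76 = 105 in Cohort 1 and 33 + 76 = 109 in Cohort 2. Both match the final visits in 4.4.

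**Placebo follow-up.** Let accrual per cohort be A = 16 to 24 weeks (4.3).
- Cohort 2: the last participant is at Week 41 and the first at Week 41 + A. Time since the last injection is 41 − 33 = 8 weeks up to 8 + 24 = 32 weeks, against 76 on active.
- Cohort 1, assuming back-to-back cohorts: participants are at Week 41 + A to 41 + 2A. Time since the last injection is 12 + A to 12 + 2A, which is 28 weeks (A = 16) up to 60 weeks (A = 24).
- Any data-cleaning lag before unblinding adds to both.

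**Model with no drug effect.** Time is counted from first injection (Week 5), so Week 41 is t = 36 and the active arm ends at 105 − 5 = 100 (Cohort 1) or 109 − 5 = 104 (Cohort 2). Let p be the risk of a first Grade 2+ event by t = 36, h = −ln(1 − p)/36, and r the tail hazard relative to h. Both arms share the same p and r:

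P(event by t) = 1 − exp[−36h − r·h·(t − 36)] for t > 36.

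**Example, Cohort 2, p = 0.50** (h = 0.6931/36 = 0.01925):
- Active, r = 1: 1 − 0.5^(104/36) = 0.865. With r = 0.5: 1 − 0.5^(1 + 34/36) = 0.740. With r = 0.25: 1 − 0.5^(1 + 17/36) = 0.640.
- Placebo, with uniform entry over A and lag L: 1 − 0.5·exp(−rhL)·[1 − exp(−rhA)]/(rhA). For r = 1, A = 16, L = 0: 1 − 0.5 × 0.861 = 0.57. For r = 1, A = 24, L = 8: 1 − 0.5 × 0.857 × 0.801 = 0.66. The corresponding ranges are 54–59% for r = 0.5 and 52–55% for r = 0.25.

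**Rejection rates.** Inputs from SAP 2.4: 82 active and 28 placebo in Cohort 1, about 66 and 22 in Cohort 2. Assumed: p = 0.2 to 0.7, L = 0 or 8 weeks, back-to-back cohorts, no dropout, two-sided 5% level. There were 4,000 simulated trials per setting for the Fisher test on the 76-week endpoint and 1,000 for the exact Poisson test. Ranges run over p and A.

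| Tail hazard | Fisher, L = 0: Cohort 2 / aggregate | Fisher, L = 8: Cohort 2 / aggregate | Rate ratio active/placebo: Cohort 2 / aggregate | Exact Poisson rejection |
|---|---|---|---|---|
| Same | 41–77% / 45–90% | 29–61% / 30–74% | 1.0 / 1.0 | 2–6% |
| Half | 15–43% / 18–58% | 12–33% / 11–42% | 0.75–0.91 / 0.82–0.94 | 7–13% |
| Quarter | 6–19% / 7–26% | 5–14% / 6–19% | 0.60–0.80 / 0.69–0.88 | 12–27% |

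The whole-study endpoint, adding the five oral-phase weeks at the same hazard and taking both lags together, gives Fisher rejection of 28–72% / 28–86%, 11–37% / 11–50% and 6–15% / 7–20% for the three hazards.

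A separate enumeration (20-week accrual, p = 0.30 to 0.85, r = 0.25 to 1, no lag) gave pooled differences of +4.7 to +20.6 percentage points. Pooled rejection was 10–83%, almost all of it towards more AEs on active. With equal observation windows the difference is zero and rejection is 3.2–4.5%.

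**The proposed replacement.** A log-rank test with both arms cut at the unblinding date rejects in 3.8–6.6% over all hazards and both lags (1,500 trials per setting).

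**The case against.** **The SAP already has a person-time analysis.** After the optional wording, 9.5.5 says without qualification that an exact interval for the rate will be produced and the arms compared by an exact Poisson test. Under a constant hazard that test is sound, and at half hazard its error is modest (7–13%). This stands as mitigation. But those sentences describe a rate that is itself only optional, the rate sits beside the Fisher test rather than replacing it, and at quarter hazard it rejects in 12–27% in the opposite direction.

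**Constant hazard is the least plausible case.** The visit list in 4.4 thins after Week 41. Cohort 2 has 15 visits over Weeks 5–41 and 6 in the next 68 weeks, a density ratio of (6/68)/(15/36) = 0.21. Cohort 1 has 11 and then 6 in 64 weeks, a ratio of 0.31. If detection followed visit density, Fisher rejection would be about 5–15% in Cohort 2 and 6–25% in aggregate. This is a fair reason to read the lower rows of the table as more likely, although AEs reported between visits would raise the figures.

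**The aggregate maximum uses a short timeline.** Two back-to-back 16-week accruals give 16 + 16 + 109 = 141 weeks, short of the stated three years; 24 weeks each gives 157. With 24 weeks, the constant-hazard aggregate maximum is about 73% without lag and 50% with it.

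**The tail may be 52 weeks.** Using the figure in 3.2 and 4.8, rejection is about 5–22% / 5–24% (Cohort 2 / aggregate) at half hazard and 4–9% / 4–11% at quarter hazard. The bias shrinks but keeps its sign.

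**Reporting is unclear.** Table 19 has no row for first injection to 76 weeks, and Section 11 names no test for it. Row (d), on-treatment, is by the definition in 7.1 the whole-study endpoint, which 9.5.5 does test.

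These points limit the size. None of them removes the bias.

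**Conclusion.** The concern holds. Whenever first Grade 2+ events occur in the tail, both crude comparisons are biased towards more AEs on active; that follows from the design alone. The size is uncertain because the SAP gives no event rates. Over the assumed risks and accrual, and both cleaning lags, Fisher rejection with no drug effect on the 76-week endpoint runs from about nominal (5%, Cohort 2, quarter tail hazard with lag) to 90% (aggregate, constant hazard, no lag). Where the rejection rate is near nominal, the point estimates are still biased.

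These are secondary endpoints and the error flags harm rather than hiding it. The primary endpoint as defined in 9.5.5 closes at Week 41 in both cohorts (29 + 12 and 33 + 8) and is essentially unaffected. This should be fixed before the final analysis.

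**What to change.** In 9.5.5, remove the between-arm Fisher test for the 76-week and whole-study proportions. Instead:

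- Compare time to first Grade 2+ event by Kaplan–Meier and log-rank test, by cohort and in aggregate. Start from first injection for the 76-week endpoint and from enrolment for the whole-study endpoint. Figure 7 already plans a time-to-first-event display for ALT/AST from these two origins.
- Censor each participant at their own last visit and cut both arms at the unblinding date. Censoring alone already deals with the unequal follow-up. The cut also keeps AEs reported open-label on active from being set against AEs reported blind on placebo, and it retains placebo follow-up after Week 41.
- Report active-arm data after the cut descriptively, with confidence intervals.
- Add person-weeks by arm and a note on unequal follow-up to Table 19(c) and (d).

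Separately, reconcile the 52-week and 76-week statements (3.2, 4.3, 4.8, 9.5.5), since the endpoint window depends on them. Also reconcile the Grade 3+ listing for Weeks 5–81 in 10.2.1 with the neighbouring tables for Weeks 5–105/109.

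The cost is SAP wording and table shells, with no new data. The crude long-term p-values are given up, and active-arm events after unblinding no longer enter a between-arm test.

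### The optional safety rate counts each participant once but does not say that person-time stops at the first event; arm comparisons beyond Week 41 also need a common follow-up

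*SAP*

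**What the plan says.** The main safety analysis in SAP Section 9.5.5 is a proportion per arm, with a Wilson interval and a Fisher test. The section then adds that "the safety endpoint rate might be calculated for each treatment arm and compared between the treatment arms". The numerator is a count of people: "The safety endpoint rate is the number of the participants who have experienced Grade 2 or higher clinical AEs or laboratory abnormalities". The denominator is described in these words: "divided by the person-time-at-risk throughout the observation period within the study period". On inference the section states "The 95% exact confidence interval of the safety event rate will be calculated for each treatment arm, assuming the rate follows the Poisson distribution" and "The safety event rate will be compared between the treatment arms using exact Poisson test". The rate is tied to the period of each safety analysis, so it can be used for the oral phase, the injection phase, the period to 76 weeks after the last injection, and the whole study.

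Follow-up is set in Section 4.3. For the active arm, "Participants in the active study product arm will be followed for 76 weeks (18 months) after their last injection". Placebo participants are followed for the same 76 weeks, "or until the last participant in the active study product arm in cohort 2 completes their Week 41 visit, whichever comes first". The section adds: "When all procedures related to unblinding are completed, participants in the placebo arm will no longer be followed". Section 4.8 gives 52 weeks, not 76, for active-arm follow-up after the last injection.

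**The concern.** A participant who has had one Grade 2 event cannot add to the numerator again. If that participant's later weeks still enter the denominator, the rate falls as follow-up lengthens, whatever the hazard. Two consequences follow.

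- **Precision.** A count of people that cannot exceed the number treated varies less than a Poisson count. Over full follow-up the exact Poisson interval is therefore too wide and the test too cautious when events are common.
- **Direction.** Where one arm is followed longer by design, that arm gets the lower rate. In the windows that include the tail, this is the active arm.

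A rate per person-time is also what a reader would turn to when follow-up is unequal, so its definition matters most in those windows.

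**Working it through.** The SAP states no rate, expected event risk or power for this analysis, so there is no planned figure to reproduce.

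**Inputs from the SAP**
- Injection-phase window: Week 5 to Week 41, so 41 − 5 = 36 weeks, not defined by arm (Section 7.1).
- Final visit: Week 105 in Cohort 1, so 105 − 5 = 100 weeks from first injection; Week 109 in Cohort 2, so 104 weeks (Section 4.4).
- Arm sizes: 82 + 66 = 148 active, 28 + 22 = 50 placebo (Section 2.4).

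**Assumptions not in the SAP**
- Constant hazard λ, equal in both arms, with 36-week Grade 2+ risk p from 20% to 80%: λ = −ln(1 − p)/36 per week.
- Placebo follow-up of 48 to 100 weeks from first injection.
- Two-sided test at 0.05.

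**1. Expected rate if time is not stopped.** Over follow-up T it is (1 − e^(−λT))/T.
- p = 60%: λ = 0.02545. Active, 100 weeks: 0.922/100 = 0.00922. Placebo, 60 weeks: 0.783/60 = 0.01305. Ratio 0.71.
- p = 20%: λ = 0.00620. Active: 0.462/100 = 0.00462. Placebo: 0.311/60 = 0.00518. Ratio 0.89.

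Active/placebo ratio with active at 100 weeks (1.00 is correct):

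| 36-week risk | Placebo 48 wk | 60 wk | 76 wk | 100 wk |
|---|---|---|---|---|
| 20% | 0.862 | 0.892 | 0.935 | 1.000 |
| 40% | 0.737 | 0.794 | 0.873 | 1.000 |
| 60% | 0.627 | 0.706 | 0.819 | 1.000 |
| 80% | 0.537 | 0.637 | 0.777 | 1.000 |

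With 36 weeks in both arms the ratio is 1.00 at every risk.

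**2. Interval and test if time is not stopped.** In a fixed window the count of affected people is binomial, with variance np(1 − p), against np under Poisson. The interval is too wide by about 1/√(1 − p): 1.12, 1.29, 1.58 and 2.24 at risks of 20, 40, 60 and 80%. Simulation (4,000 runs, 148 versus 50, equal hazards) gives:

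| 36-week risk | Width vs correct, 36/36 wk | Test size, 36/36 wk | Width vs correct, 100/60 wk | Test size, 100/60 wk |
|---|---|---|---|---|
| 20% | 1.17 | 0.020 | 1.40 | 0.018 |
| 40% | 1.35 | 0.006 | 2.10 | 0.064 |
| 60% | 1.64 | 0.001 | 3.58 | 0.365 |
| 80% | 2.28 | 0.000 | 9.77 | 0.975 |

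Widths are for the active arm. With unequal follow-up and common events, the bias outweighs the excess width and the test rejects falsely.

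**3. Time stopped at the first event, constant hazard.** In the same simulations, with risks up to 90%, the median rate ratio is 1.00 to 1.01, coverage 0.954 to 0.960, width 0.99 to 1.05 times the correct one, and test size 0.035 to 0.045. This holds for 36/36 and for 100/60 weeks.

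**4. Time stopped at the first event, hazard halved after Week 41 (assumed).** With S = 1 − p:
- events per participant = 1 − S·e^(−λ(T − 36)/2);
- person-time = (1 − S)/λ + S·(1 − e^(−λ(T − 36)/2))/(λ/2).

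At p = 20%, active gives 0.3439/78.71 = 0.00437 and placebo 0.2573/50.77 = 0.00507, ratio 0.86. At 40, 60 and 80% the ratio is 0.88, 0.90 and 0.94. Stopping time at the first event does not by itself make windows of different length comparable.

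**5. Effect of the 52/76-week conflict.** In Cohort 1, 52 weeks after Week 29 is Week 81, which is 76 weeks from first injection. From the table, the 76 versus 60 week ratio is 0.892/0.935 = 0.95 at 20% risk and 0.706/0.819 = 0.86 at 60%. The imbalance is smaller but not gone.

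**The case against.** The case for leaving the text alone has four parts.

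- **The at-risk qualifier.** With a once-only numerator, time at risk can naturally mean time to first event, and the rest of the phrase may only bound the window. The HIV incidence rate in Section 9.11 uses accumulated person-years without that qualifier, which fits this reading. This stands: the text is ambiguous, and on this reading the Poisson interval and test are sound.
- **The analysis is optional.** The rate supplements the proportions. Table 19 in Section 11.2.1 presents proportions, and neither that list nor the closed-report list in Section 10.2.1 contains a safety rate. This stands and limits the weight of the point.
- **The primary window is not biased.** The oral and injection-phase windows do not differ by arm. This stands; there the only cost is a conservative interval and test.
- **Short placebo follow-up is an extreme.** Placebo participants stay until the last active Cohort 2 participant reaches Week 41, so earlier enrollees, and Cohort 1 in particular, should have well over 36 weeks. This stands, and is why the ratios are shown over a range.

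A reader might go further and infer that the SAP fixes full follow-up as the denominator, or that harm would be hidden. The documents support neither. The wording does not settle the denominator. The main comparison in the same tail-inclusive windows is the proportion, which unequal follow-up pushes the other way: at 60% risk, 92% active against 78% placebo with no true difference.

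The objection does not dispose of the need for common follow-up. Step 4 shows a ratio below 1 even on the favourable reading if the hazard falls after Week 41.

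**Conclusion.** The denominator of the supplementary safety rate is not fixed, and one permitted reading conflicts with the prescribed Poisson method. On that reading:

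- In the equal-length oral and injection-phase windows the interval is too wide and the test conservative, without directional bias. In the 36-week injection phase the interval is 1.17 to 2.28 times the correct width at risks of 20% to 80%.
- In the 76-week and whole-study windows the active arm's rate is understated relative to placebo. For 100 versus 60 weeks the ratio is 0.89 at 20% risk and 0.71 at 60%. It moves towards 1.00 as placebo follow-up approaches 100 weeks.

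On the time-to-first-event reading neither problem arises under a constant hazard, but comparability beyond Week 41 still depends on the hazard not changing. All sizes rest on assumed hazards and placebo follow-up times. This is a definition worth fixing in an optional analysis; it does not show that the primary safety comparison is biased.

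**What to change.** In Section 9.5.5, state that each participant's person-time runs from the start of the analysis period to the first Grade 2 or higher event in it, or to the end of the phase or of follow-up if earlier.

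For windows beyond Week 41, compare arms only over common blinded follow-up, for example by censoring both arms at unblinding, or use a time-to-first-event method truncated there. Apply the same limit to the proportions for those windows. Describe later active-arm data without a between-arm comparison.

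Reconcile Sections 4.3 and 4.8 on the length of active-arm follow-up, since it sets the size of the imbalance.

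The cost is a few sentences. The AE phase algorithm in the SAP Appendix already uses onset dates; where only the day is missing, a rule for placing the event in time is needed. The one loss is that active-arm data after unblinding leave the between-arm comparison.

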9.5.6 Reasons for Treatment Discontinuation and Early Study Termination

The number and percentage of participants who discontinue the study treatment and who terminate the study early will be tabulated by reasons and the treatment arm separately for the oral phase and the injection phase by cohort and in aggregate.

9.6 Tolerability

To assess tolerability of 744 LA, the proportion (with 95% CI) of subjects who terminate from receiving injections prior to the full course due to AEs, intolerance of injection, frequency of injections, or burden of procedures related to injections out of those subjects that received at least one injection by cohort and treatment arm will be provided. The proportion will be compared between the treatment arms by cohort and in aggregate using Fisher Exact test.

9.7 Pharmacokinetics

Plasma GSK1265744 concentration-time data will be analyzed by noncompartmental methods using WinNonlin Professional 5.2 or higher, Phoenix (Pharsight Corporation) or comparable software. Individual plasma PK parameters for each injection interval will be determined which include the area under the plasma concentration time curve over the dosing interval ($AUC(0-\tau)$), maximum observed concentration (C_{max}), time to maximum observed concentration (t_{max}), concentration at the end of the dosing interval (C_τ), apparent terminal phase half-life for 744LA administration ($t_{1/2}$) and lambda z as a measure of absorption rate constant (λ_z) if data allow among the participants in the 744 arm. The pharmacokinetic parameters will be generated by the scientist from HPTN Core Laboratory.

The summary statistics of pharmacokinetic parameters, $AUC(0-\tau)$, C_{max} , and C_τ , will be presented by injection. The means of the pharmacokinetic parameters (after log-transformation) and their 95% CIs will be displayed by visit weeks and cohort. The pharmacokinetic parameters, $AUC(0-\tau)$, C_{max} , and C_τ in different injection intervals will be compared using paired t-test if the data or log transferred data appear to be normally distributed and using Wilcoxon signed rank test if the data or log transferred data are not normally distributed.

Time to steady state will also be assessed by comparing plasma concentration, C_τ , at Week 41 (following third injection) to previous C_τ concentrations at Weeks 17 and 29 (at Weeks 17, 25, and 29) in Cohort 1 (Cohort 2). General estimation equation (GEE) regression model will be used to test any difference in the concentration over time and a trend.

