2.2 Primary Objectives

- Evaluate the safety and tolerability of the injectable agent GSK1265744 long acting (744LA) injectable (800 mg dose administered at three time points at 12 week intervals), through Week 41 in HIV-uninfected men and women.
- Evaluate the safety and tolerability of the injectable agent GSK1265744 long acting (744LA) injectable (600 mg dose administered at two time points at 4 week intervals, followed by three time points at 8 week intervals), through Week 41 in HIV-uninfected men and women.

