2.3 Study Product Regimens/Administration/Formulation Content

Study Product Regimens

Both Cohorts:

Oral lead-in phase: Participants will be randomized 3:1 to one of two study arms:

- Arm 1: GSK1265744 tablets 30 mg – one tablet orally daily for 4 weeks, with or without food
- Arm 2: Placebo for GSK1265744 – one tablet orally daily for 4 weeks, with or without food

Injectable phase: After a one week washout period to assess safety, participants will begin injections (with the same randomization as the oral lead-in phase) as:

Cohort 1:

- Arm 1: GSK1265744 (744 LA) 800 mg administered as two 2 mL (400 mg) IM injections in the gluteal muscle at Weeks 5, 17, and 29

- Arm 2: Placebo for GSK1265744 (744 LA Placebo) administered as two 2 mL injections in the gluteal muscle at Weeks 5, 17, and 29

Cohort 2:

- Arm 1: GSK1265744 (744 LA) 600 mg administered as one 3mL (600 mg) IM injections in the gluteal muscle at Weeks 5, 9, 17, 25 and 33
- Arm 2: Placebo for GSK1265744 (744 LA Placebo) administered as one 3 mL injections in the gluteal muscle at Weeks 5, 9, 17, 25 and 33

Study Product Formulations

Oral product:

- GSK1265744 tablets 30 mg are formulated as white to almost white oval-shaped coated tablets for oral administration. The tablets are packaged in high density polyethylene (HDPE) bottles with child-resistant closure that include an induction seal. The bottles contain a desiccant. The bottles should be stored up to 25 degrees Celsius (25° C) and protected from moisture.
- Placebo tablets for GSK1265744 are formulated as white to almost white oval-shaped coated tablets to visually match the active GSK1265744 tablets. The tablets are packaged in high density polyethylene (HDPE) bottles with child-resistant closure that include an induction seal. The bottles contain a desiccant. The bottles should be stored up to 25 degrees Celsius (25° C) and protected from moisture.

Injectable Suspension:

[figure not shown]
- The GSK1265744LA is formulated as a sterile white to slightly colored suspension containing 400mg/2mL of GSK1265744 for administration by intramuscular (IM). The product is packaged in a 3 mL vials. Each vial is for single use containing a nominal fill of 2mL (400 mg), and does not require dilution prior to administration. The GSK1265744LA injectable suspension is to be stored at 2 degrees Celsius to 30 degrees Celsius (2° C – 30° C), do not freeze.

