4.4 Study Visits

Cohort 1:

- Week 0: enrollment visit
- Weeks 2 and 4: oral phase safety visits
- Week 5: the first injection visit
- Weeks 6, 9, 13: safety visits after the 1st injection
- Week 17: the second injection visit
- Weeks 18 and 23: safety visits after the 2nd injection
- Week 29: the third injection
- Weeks 30, and 35: safety visits after the 3rd injection
- Week 41: primary endpoint visit
- Weeks 53, 65, 77, 89, 101: tail phase safety visit
- Week 105: final study visit.

Cohort 2:

- Week 0: enrollment visit
- Weeks 2 and 4: oral phase safety visits
- Week 5: the first injection visit
- Week 6: safety visits after the 1st injection
- Week 9: the second injection visit
- Weeks 10 and 13: safety visits after the 2nd injection
- Week 17: the third injection visit
- Weeks 18 and 21: safety visits after the 3rd injection
- Week 25: the forth injection
- Weeks 26, and 29: safety visits after the 4th injection
- Week 33: the fifth injection visit
- Week 34 and 37: safety visits after the 5th injection
- Week 41: primary endpoint visit
- Weeks 53, 65, 77, 89, 101: tail phase safety visit
- Week 109: final study visit.

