9.7.1 Association between Pharmacokinetics and Baseline Characteristics

To evaluate differential pharmacokinetics of 744LA in participants by age, gender, race, ethnicity, weight, body mass index (BMI), and smoking status, we will use GEE regression model to account the correlations of the PK parameters following three injections in Cohort 1 or five injections in Cohort 2. The analysis will be performed separately for each cohort. The associations between the PK parameters and the predictors will be tested in univariate models (include one predictor in each model) and

in a multivariate model (include all predictors). Each model will be adjusted for sites (US vs. Non-US sites) by cohort.

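### In Cohort 2 the paired AUC(0-τ) and C-τ tests set a 4-week first interval against 8-week intervals, which builds a factor of 2 into AUC

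*SAP*

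**What the plan says.** SAP section 9.7 defines AUC(0-τ) as the area over the dosing interval and C-τ as the concentration at its end, both derived for each injection interval. It names these two together with Cmax, stating that their values "in different injection intervals will be compared using paired t-test if the data or log transferred data appear to be normally distributed"; otherwise the Wilcoxon signed-rank test applies. It does not say which pairs of intervals are meant, and it makes no distinction between cohorts.

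The two cohorts have different calendars. In section 2.3, Cohort 1 receives "two 2 mL (400 mg) IM injections in the gluteal muscle at Weeks 5, 17, and 29", and Cohort 2 receives "IM injections in the gluteal muscle at Weeks 5, 9, 17, 25 and 33". Section 4.4 agrees for Cohort 2 ("Week 9: the second injection visit"), and section 2.2 describes the regimen as "600 mg dose administered at two time points at 4 week intervals, followed by three time points at 8 week intervals". The last Cohort 2 interval closes at the Week 41 visit, 8 weeks after the Week 33 injection, which matches the Cohort 2 window in section 9.5.5.

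Section 9.7.1 uses a separate model for each cohort, a GEE to "account the correlations of the PK parameters following three injections in Cohort 1 or five injections in Cohort 2". The covariates it states are the predictors and region: "Each model will be adjusted for sites (US vs. Non-US sites) by cohort".

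**The concern.** A paired comparison between intervals is informative about accumulation only if the quantity has the same meaning in each interval. In Cohort 1 it does. In Cohort 2, the first interval's AUC is an area over 4 weeks and the later ones are areas over 8 weeks. The first C-τ is a 4-week level and the later ones are 8-week levels. A significant result that involves interval 1 would then mainly report the injection calendar, yet it could be taken as a finding about the drug's kinetics.

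The unequal pair is not a remote case. Section 5.2 plans a Cohort 2 PK analysis when about half the cohort reaches Week 17, described as two troughs. A participant who has just reached Week 17 has completed only intervals 1 and 2, so the only pair available is the unequal one. Section 5.2 does not say that the paired tests will be run then. It does say that PK summaries may go to the protocol team and to regulators to help start a phase III trial.

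**Working it through.** **Interval lengths, from the stated weeks.**
- Cohort 2: 9−5 = 4, 17−9 = 8, 25−17 = 8, 33−25 = 8. These sum to 28 weeks, the figure in section 4.3. The last interval is 41−33 = 8.
- Cohort 1: 17−5 = 12, 29−17 = 12, 41−29 = 12. The first two sum to the 24 weeks in section 4.3.
- Five Cohort 2 intervals give 10 pairs, of which 4 contain interval 1.

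**AUC with average concentration unchanged.** AUC(0-τ) = Cavg × τ, so the ratio of an 8-week interval to the 4-week interval is 8/4 = 2. This needs no PK assumption.

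**Chance that the paired t-test on log AUC rejects on that factor alone** (two-sided 5% level, assumed). The SD of the paired log difference is √2 × √ln(1+CV²), and the noncentrality is ln 2 × √n / SD. The SAP gives no within-person CV, so 50% and 80% are assumed.
- CV 80%: SD = 1.414 × 0.703 = 0.995. At n = 20 the noncentrality is 0.693 × 4.472 / 0.995 = 3.12 and power is 84%.
- CV 50%: SD = 1.414 × 0.472 = 0.668. At n = 20 the noncentrality is 4.64 and power is 99%.
- At n = 66, the approximate Cohort 2 active arm in section 2.4, power exceeds 99.9% with either CV.

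**What the raw ratios would show under simple kinetics.** The SAP gives no half-life, so apparent half-lives of 4 to 12 weeks are assumed. Equal doses decay mono-exponentially, and any drug left from the oral lead-in is ignored. Let x be the fraction remaining after 4 weeks and S the level just after each injection: S1 = 1, S2 = 1 + x, then S(j+1) = 1 + x²·S(j). The ratios to interval 1 are:
- AUC, interval 2: (1+x)²
- AUC, interval 5: S5(1+x), and AUC/τ is half of that
- C-τ, interval 5: S5·x² / x = S5·x
- level 4 weeks after injection 5 against 4 weeks after injection 1: S5

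| Half-life (weeks) | x | S5 | AUC 2/1 | AUC 5/1 | AUC/τ 5/1 | C-τ 5/1 | 4-week level 5/1 |
|---|---|---|---|---|---|---|---|
| 4 | 0.500 | 1.336 | 2.25 | 2.00 | 1.00 | 0.67 | 1.34 |
| 6 | 0.630 | 1.656 | 2.66 | 2.70 | 1.35 | 1.04 | 1.66 |
| 8 | 0.707 | 1.963 | 2.91 | 3.35 | 1.68 | 1.39 | 1.96 |
| 12 | 0.794 | 2.475 | 3.22 | 4.44 | 2.22 | 1.96 | 2.48 |

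At a 4-week half-life the raw tests would report doubled AUC and a trough lower by a third. Average concentration is unchanged, and the like-for-like 4-week level has risen by a third. At longer half-lives accumulation is real, but raw AUC overstates the rise in average concentration by a factor of 2.

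**A second model as a check.** With first-order absorption and elimination (terminal half-life 2 to 12 weeks, fast phase 0.25 to 1 week, both assumed), interval 5 against interval 1 gives 1.40 to 6.50 for raw AUC, 0.70 to 3.25 for AUC/τ and 0.27 to 2.13 for C-τ. At a 2-week half-life raw AUC rises (1.40 to 1.78) while AUC/τ falls (0.70 to 0.89). Among the 8-week intervals, AUC in interval 5 against interval 2 is 0.78 to 1.45, which has no interval-length component.

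**The case against.** **Already handled in part.** The time-to-steady-state analysis in section 9.7 does not list Week 9 for Cohort 2, so it avoids the 4-week trough. Summaries are given by injection, so unlike intervals are not averaged there. The plan names no interval pairs, and a sensible analyst might leave interval 1 out. All of this stands and limits the reach of the problem. It does not change the paired tests, whose wording covers interval 1.

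**C-τ.** C-τ is the trough at the end of the interval. If it is lower after 8 weeks than after 4, the trough did fall, and that is a legitimate description of the regimen. This stands. A reader might infer that the plan will manufacture a falling C-τ. The table does not support that: the ratio falls at a 4-week half-life, is about level at 6 weeks, and rises at 8 and 12. What fails is reading the contrast, in either direction, as evidence on accumulation.

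**Section 9.7.1.** A reader might infer that pooling five unlike intervals without a term for injection number distorts the covariate associations or shows a false time trend. The document does not support this. That model compares nothing over time. Its predictors are participant characteristics, cohorts are modelled separately, and every Cohort 2 participant has the same calendar. Unequal length alone puts an SD of ln 2 × √(0.2 × 0.8) = 0.28 on the log AUC values within a participant, but the pattern is the same in everyone and cancels from a between-participant contrast. In a simulation on the log scale (66 participants, binary covariate, half-life 6 weeks, between- and within-person SD 0.4, all but the sample size assumed), the mean robust SE with complete data was 0.1064 with or without injection number. With 10% stopping after injection 1 it was 0.112 without the term and 0.108 with it. Section 9.7.1 does not state the scale, and on the raw scale the cancellation is not exact.

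**Weight.** PK is a secondary objective in section 3.2, whose general PK objective names only the 800 mg regimen. No alpha or decision rule is attached to these tests. This stands and sets the severity.

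**Conclusion.** The point holds for the paired comparisons in section 9.7, in Cohort 2 only. Any paired AUC(0-τ) test that includes interval 1 has a factor of 2 built in by the calendar. Such a test is close to certain to reject at the planned arm size even if average concentration does not change. The factor of 2 follows from the injection weeks alone. The rejection probabilities rest on an assumed CV of 50% to 80%, and the fold changes beyond 2 rest on assumed half-lives. For C-τ, the contrast with interval 1 is valid as a description but uninformative about accumulation or decline. Cohort 1, the Cohort 2 pairs among injections 2 to 5, and the covariate models on the log scale are not materially affected. The wording should be fixed before the PK tests are run. It does not bear on the primary safety and tolerability endpoints.

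**What to change.** In section 9.7, state that for Cohort 2 the paired AUC(0-τ) and C-τ tests are restricted to the 8-week intervals (injections 2 to 5). If interval 1 is included, compare AUC(0-τ)/τ and describe the result as average exposure over the interval. It is not a pure measure of accumulation, since one average covers 4 weeks after a dose and the other 8 (in the table, AUC/τ is 1.00 while the 4-week level is 1.34). Report the interval 1 C-τ contrast only as a description of the regimen's troughs. Cohort 1 needs no change.

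Adding injection number as a categorical term to the Cohort 2 GEE in section 9.7.1 is optional. On the log scale it changes nothing with complete data and gains a few percent in precision when some participants stop early.

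The cost is a sentence or two in the SAP and a few lines of code, with no new data. The four interval pairs that contain interval 1 drop out of the unscaled tests, and six pairs remain.
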